3.5.2. Exposure

Human exposures have been estimated from the pharmacokinetics in the cynomolgus monkey since a non-human primate represents the most closely related species. Approximately dose-proportional exposure was seen in the 13-week toxicity study (Covance study no. 8355565) and ¹⁴C pharmacokinetic study (Covance study no. 8355568) over a dose range of approximately 1.1 to 100 nmol/kg (5.06 to 462.29 µg/kg)⁴. However, the lowest dose (5.06 µg/kg) from the ¹⁴C study has been used to estimate the human exposures as it is closest to the proposed human dose range and has the sufficient quantifiable data.

The assumptions made in the human exposure estimation were that human exposure would be similar to the cynomolgus monkey and that exposure would be linear with dose. Following a dose of 5.06 µg/kg in the cynomolgus monkey, the C_{max} was 1.96 ng/mL and AUC_{0-∞} was 12.7 ng.h/mL. The extrapolated exposures at the planned human doses are shown in [Table 1](#) with margins calculated to the exposures at the NOAEL in the female rat.

Table 1: Estimated Human Exposure and Safety Margins to the NOAEL in the Female Rat for Single Dose Administration of OLP-1002

Human dose		Single dose to human		Safety margins for single dose	
(µg)	(µg/kg)	Predicted C _{max} (ng/mL)	Predicted AUC _{0-∞} (ng.h/mL)	Margin to C _{max}	Margin to AUC _{0-∞}
0.03	0.000500	0.000194	0.00125	129000	102000
0.12	0.00200	0.000775	0.00502	32100	25500
0.4	0.00667	0.00258	0.0167	9640	7650
1.2	0.0200	0.0077	0.0502	3210	2550
3	0.0500	0.0194	0.125	1290	1020
6	0.100	0.0387	0.251	643	510
12	0.200	0.0775	0.502	321	255
20	0.333	0.129	0.837	193	153

Abbreviations: AUC_{0-∞} = area under the plasma concentration-time curve extrapolated to infinity; C_{max} = maximum observed plasma concentration.

The dosing interval currently anticipated for the multiple-ascending-dose part of this study is 72 hours or 96 hours. Thus the average dosing interval (82 hours) is similar to the half-life determined in the monkey ¹⁴C study of 84 hours. Dosing at approximately once per half-life would be anticipated to result in accumulation of around 2-fold. However, higher levels of accumulation were observed (2.28-fold for C_{max} and 3.76-fold for AUC₀₋₂₄) on Day 88 at the top dose group (100 nmol/kg, 462.28 µg/kg) in the 13-week cynomolgus monkey toxicity study following twice-weekly dosing (every 72 or 96 hours). Calculations were performed to estimate the likely human half-life using a standard 1-point allometric approach from the ¹⁴C cynomolgus monkey pharmacokinetic study data. The exponents used were 0.75 for apparent total plasma clearance (CL/F) and 1 for apparent volume of distribution (V_z/F) values combined with the average body weight of the animal (3.1 kg) and scaling to a 60 kg human⁹⁻¹¹. This resulted in a human half-life estimate of 180 h which in turn gave an accumulation estimate of 3.7-fold based upon a dosing interval of 82 h. This further supports the use of the greater than 2-fold accumulation from the 13-week cynomolgus study to estimate exposure following multiple dosing. Multiplication of the exposure estimates for the single ascending

dose by 2.28 for C_{max} and 3.76 for AUC resulted in exposure estimates for multiple dosing presented in [Table 2](#).

Table 2: Estimated Human Exposure and Safety Margin to the NOAEL in the Female Rat for Multiple Dose Administration of OLP-1002

Human dose		Multiple dose to human		Safety margins for multiple dose	
(μg)	($\mu\text{g}/\text{kg}$)	Predicted C_{max} (ng/mL)	Predicted $AUC_{0-\infty}$ (ng.h/mL)	Margin to C_{max}	Margin to $AUC_{0-t,ss}$
0.03	0.000500	0.000442	0.00472	56000	27000
0.12	0.00200	0.00177	0.0189	14100	6800
0.4	0.00667	0.00589	0.0629	4230	2030
1.2	0.0200	0.017663	0.189	1410	680
3	0.0500	0.0442	0.472	560	270
6	0.100	0.0883	0.944	282	136
12	0.200	0.177	1.89	141	68
20	0.333	0.294	3.15	85	41
30	0.500	0.442	4.72	56	27

Abbreviations: $AUC_{0-\infty}$ = area under the plasma concentration-time curve extrapolated to infinity; C_{max} = maximum observed plasma concentration.

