Pharmacokinetic analysis in Part A will initially only be conducted for groups receiving $\geq 12 \mu\text{g}$ OLP-1002, with retrospective analyses of samples from lower dose groups occurring in the event of PK data being quantifiable at doses $\geq 12 \mu\text{g}$ and if supported by bioanalytical stability data. Dose escalation decisions for doses $< 12 \mu\text{g}$ in Part A will not require PK data. The rationale for this is that maximum plasma concentrations at $12 \mu\text{g}$ are expected to be approximately 0.078 ng/mL and the bioanalytical method used for preclinical species has a lower limit of quantification (LLOQ) of 5 ng/mL. The increased sample volume possible from humans (compared to small animals) may afford an approximate 10-fold increase in sensitivity with possibly an additional 5-fold increase from the use of a more sensitive mass spectrometer. This could potentially deliver an LLOQ of around 0.1 ng/mL. Therefore, even with the increased assay sensitivity plasma levels from doses at or below $12 \mu\text{g}$ are not expected to be quantifiable. It is apparent from the predicted plasma concentrations (see [Section 3.5.2](#)) that only a small number of samples around C_{max} at the highest dose would be quantifiable and that a conventional approach to pharmacokinetic will not achieve a full definition of the plasma concentration vs time profile or enable an estimation of the terminal phase. In addition the planned dose levels have a high safety margin when comparing the predicted exposures to the exposures at the NOAEL (see [Section 3.5.2](#)), with the $12 \mu\text{g}$ dose level having an expected 312-fold and 255-fold safety margin based on C_{max} and $AUC_{0-\infty}$, respectively. Therefore, if exposure is significantly higher than predicted it is not expected to exceed the PK stopping criteria.

This study will be double-blind and placebo-controlled in order to avoid bias in the collection and evaluation of data during its conduct. Placebo has been chosen as the control treatment to assess whether any observed effects are treatment-related or simply reflect the study conditions.

Conducting the study in healthy subjects mitigates the potential confounding effects of the disease state and concomitant medications.

Continuous ECG monitoring will be recorded in this study and archived for potential future analysis of OLP-1002 effects on the QT interval, with a view of supporting a potential thorough QT study waiver.

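### Section 3.5.2 uses two incompatible human clearances; under its own 0.75 exponent the Table 1 single-dose AUC margins are about half those stated (153 becomes 73 at 20 µg, 255 becomes 122 at 12 µg)

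*Protocol*

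**What the plan says.** Protocol Section 3.5.2 makes two predictions from one ¹⁴C study in cynomolgus monkeys.

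- **Exposure (Table 1).** The starting data are: "Following a dose of 5.06 µg/kg in the cynomolgus monkey, the C_{max} was 1.96 ng/mL and AUC_{0-∞} was 12.7 ng.h/mL". The stated assumptions are that "human exposure would be similar to the cynomolgus monkey and that exposure would be linear with dose". Table 1 gives an AUC0-∞ of 0.837 ng.h/mL and an AUC margin of 153 at 20 µg, and 0.502 ng.h/mL and 255 at 12 µg. The margins are taken against the female rat NOAEL exposure, which Section 3.5.1 gives as an AUC0-24 of 128 ng.h/mL.
- **Half-life.** The monkey half-life of 84 h is scaled allometrically: "The exponents used were 0.75 for apparent total plasma clearance (CL/F) and 1 for apparent volume of distribution", "combined with the average body weight of the animal (3.1 kg) and scaling to a 60 kg human". The outcome is stated as: "This resulted in a human half-life estimate of 180 h". It leads to an "accumulation estimate of 3.7-fold based upon a dosing interval of 82 h".

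Table 2 multiplies the Table 1 AUC by 3.76, an accumulation factor observed in the 13-week monkey study.

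Section 3.4 cites the 12 µg row of Table 1 when explaining why escalation below 12 µg does not need PK data. Its sentence pairs one figure with Cmax and a "255-fold safety margin based on" AUC0-∞. It then concludes that even a markedly higher exposure than predicted should not reach the PK stopping criteria.

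**The concern.** Equal AUC per µg/kg in two species means equal CL/F per kg, that is, a clearance exponent of 1. An exponent of 0.75 means that CL/F per kg falls as body weight rises. With the volume exponent at 1, that fall is the only reason the half-life lengthens from 84 h to about 180 h. A reader who accepts the 180 h has accepted a lower human clearance, and a lower clearance raises AUC by the same factor. The AUC column of Table 1 does not reflect this.

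Both results are used. The Table 1 AUC margin supports the statements in Section 3.4. The 180 h half-life supports the review windows in Section 3.4 and the accumulation assumption in Section 3.4.1. The safety rationale therefore rests on two human clearances that differ about two-fold. Each is stated openly, but nowhere are they reconciled.

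**Working it through.** **Inputs.** Monkey dose 5.06 µg/kg, AUC0-∞ 12.7 ng.h/mL, half-life 84 h, weight 3.1 kg; human weight 60 kg; exponents 0.75 (CL/F) and 1 (Vz/F); multiple-dose AUC factor 3.76 (all Section 3.5.2). Rat NOAEL AUC0-24 128 ng.h/mL (Section 3.5.1).

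**1. Reproduce Table 1.** AUC = (12.7/5.06) × dose/60; margin = 128/AUC.
- 20 µg: 2.510 × 0.333 = 0.837; 128/0.837 = 153. Agrees.
- 12 µg: 2.510 × 0.200 = 0.502; 128/0.502 = 255. Agrees.

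**2. Clearance implied by Table 1.** CL/F per kg = 5.06/12.7 = 0.398 L/h/kg in both species. At 60 kg this is 0.398 × 60 = 23.9 L/h.

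**3. Reproduce the half-life.** 84 × (60/3.1)^(1 − 0.75) = 84 × 2.097 = 176 h, against 180 h stated (about 2% apart). Accumulation at 180 h and an 82 h interval: 1/(1 − 2^(−82/180)) = 3.69, against 3.7 stated.

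**4. Clearance implied by the half-life.** Monkey CL/F = 0.398 × 3.1 = 1.235 L/h. Human CL/F = 1.235 × (60/3.1)^0.75 = 11.4 L/h. The ratio to step 2 is 23.9/11.4 = 2.10, the same factor as in step 3.

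**5. Table 1 with the 0.75 exponent.** AUC0-∞ = dose/11.4; every AUC in the table rises, and every AUC margin falls, by 2.10.

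| Dose | AUC0-∞ stated | AUC0-∞ at exponent 0.75 | Margin stated | Margin at exponent 0.75 |
|---|---|---|---|---|
| 6 µg | 0.251 | 0.526 | 510 | 243 |
| 12 µg | 0.502 | 1.053 | 255 | 122 |
| 20 µg | 0.837 | 1.755 | 153 | 73 |

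With the rounded ratio 180/84 = 2.14 in place of 2.10, the last two margins are 119 and 71.

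**6. Converse check.** With both exponents at 1, the human half-life would stay at 84 h. No single scaling gives both 180 h and an AUC0-∞ of 0.837 ng.h/mL at 20 µg.

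**7. Table 2.** As tabulated, 0.8366 × 3.76 = 3.146 ng.h/mL at 20 µg and 128/3.146 = 41. The margin column is labelled as steady-state AUC0-τ. Under the linear kinetics that Section 3.5.2 assumes, this equals the single-dose AUC0-∞. With exponent 0.75 it is therefore 1.755 ng.h/mL, a margin of 73, which is more favourable than the 41 printed.

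**The case against.** **The tables contain no slip.** The Table 1 and Table 2 AUC entries reproduce to rounding, and the exposure step is labelled as an assumption. This stands: the fault is an inconsistency between two stated assumptions, not a miscalculation.

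**Table 2.** A reader might infer that the factor also halves the Table 2 margins, for example from 41 to 128/(3.146 × 2.097) = 19 at 20 µg. The documents do not support that. It counts slower clearance and then multiplies by 3.76 on top, although linear kinetics already fixes steady-state AUC0-τ at the single-dose AUC0-∞ (step 7). The 3.76 step is conservative and more than offsets the scaling.

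**The metric.** Both the rat comparator and the Section 3.7 stopping limit are AUC0-24, whereas Table 1 gives human AUC0-∞. Human AUC0-24 cannot exceed AUC0-∞, so 73 and 122 are floors, and the change in AUC0-24 may be well below 2.1-fold. As illustration only, a one-compartment decline gives AUC0-24 at 20 µg of 0.837 × (1 − 2^(−24/84)) = 0.150 against 1.755 × (1 − 2^(−24/176)) = 0.158, about 5% apart. The monkey data do not fit one compartment: Vz/F is 0.398 × 84/0.693 = 48 L/kg, while dose/Cmax is 5.06/1.96 = 2.6 L/kg. The real offset cannot be sized without a concentration-time profile. For the same reason nothing is claimed here about the Cmax margins.

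**Weight in the rationale.** Section 3.4 rests mainly on a predicted Cmax at 12 µg (0.078 ng/mL) below the hoped-for LLOQ (0.1 ng/mL); the margins are an added argument. Section 3.5.1 gives a separate dose-based margin of 22-fold for 20 µg, already tighter than 73. This also stands. A reader might infer that the choice of maximum dose depends on the AUC margins, or that a limit is at risk; neither follows.

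**Selective scaling.** A reader might infer that the convenient scaling was chosen each time. For half-life and accumulation the 0.75 exponent is the more cautious choice, so the documents do not bear that out.

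**Conclusion.** The inconsistency is real and of known size on the metric that Table 1 reports. Under the protocol's own 0.75 exponent, single-dose human AUC0-∞ is 2.1-fold higher than tabulated, and the AUC margins become at least about 73 at 20 µg and 122 at 12 µg instead of 153 and 255. This rests on the monkey weight, human weight and exponents as stated, on linear kinetics, and on the same ¹⁴C study serving both predictions, all of which Section 3.5.2 sets out.

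The finding is confined to the AUC column and AUC margins of Table 1 and to the 255-fold figure in Section 3.4. The margins remain far above 1. It is a defect in how the exposure rationale is stated, not evidence that exposure would approach the stopping limits. It is worth correcting because the safety argument cites the figure and the correction is nearly free.

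**What to change.** 1. In Section 3.5.2, reconcile the exposure assumption with the half-life derivation. Restate the Table 1 AUC column and AUC margins under the 0.75 exponent, or print both scalings as a range (for example 73 to 153 at 20 µg and 122 to 255 at 12 µg).
2. Carry the result into the Section 3.4 sentence. That sentence needs editing anyway: it gives 312-fold for Cmax at 12 µg where Table 1 gives 321 (24.9/0.0775 = 321).
3. State that the margins set a human AUC0-∞ against a rat AUC0-24, and that this understates the margin.

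The passages need to be made consistent. No dose, half-life, accumulation assumption or review window is proposed or preferred here. In particular, replacing 180 h with 84 h and about 2-fold accumulation is not suggested: it would set aside the 2.28- and 3.76-fold accumulation observed in the 13-week monkey study and would touch assumptions behind Part B dosing.

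The cost is one table column, its margins and one sentence. The only downside is that the printed margins look less favourable.

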3.5.3. Proposed Doses

The proposed IMP dose levels for Parts A and B are shown in [Table 3](#).

Table 3: Proposed Investigational Medicinal Product Dose Levels for Parts A and B

Study Part	Group	Dose (OLP-1002)
Part A	A1	30 ng or placebo
	A2	120 ng or placebo
	A3	400 ng or placebo
	A4	1.2 μg or placebo
	A5	3 μg or placebo
	A6	6 μg or placebo
	A7	12 μg or placebo
	A8	20 μg or placebo
	A9*	TBC or placebo
	A10*	TBC or placebo
	A11*	TBC or placebo
Part B	B1	TBC or placebo
	B2	TBC or placebo
	B3	TBC or placebo
	B4*	TBC or placebo
	B5*	TBC or placebo
	B6*	TBC or placebo

Abbreviations: TBC = to be confirmed
* groups to be included if required.

In Parts A and B, there should not be an increase of > 3-fold between dose levels above 120 ng.

For Part B, dose levels, dosing frequency, and dosing duration will be decided, in consultation with the Sponsor, on the basis of data from Part A of the study. Since predictions of human exposure of OLP-1002 suggest that OLP-1002 concentrations may be not be quantifiable and human data have been estimated from a single species, it is proposed that the highest dose in the multiple-ascending-dose part will be up to 50% of the highest dose in the single-ascending-dose part (ie, if the highest dose in the single-ascending-dose part is 20 µg, the highest dose in the multiple-ascending-dose part will be 10 µg). Therefore, if the predicted accumulation of 3.7-fold occurs, the highest exposure in the multiple-ascending-dose part will not exceed ~2-fold the maximum exposure in the single-ascending-dose part.

If additional groups (A9-11 or B3-6) are required, the maximum daily dose administered will not exceed 20 µg and predicted systemic exposure will not exceed that stated in the dose escalation stopping criteria [[Section 3.7](#)] based on available PK data.

Details of all doses administered in Parts A and B of the study will be documented in the TMF.

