3.3. Additional Groups

Following review of the safety, tolerability, PK, and PD data (where systemic exposure is not expected to exceed that stated in the dose escalation stopping criteria [[Section 3.7](#)]), additional dose groups may be added to the study. The maximum dose for any additional group will not exceed 20 µg. Up to 3 further groups of 8 subjects (6 active: 2 placebo) may be included in Part A, and up to 3 additional groups of 8 subjects (6 active: 2 placebo) may be included in Part B. The requirement for additional groups will be agreed with the Sponsor and documented in the Trial Master File (TMF).

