Investigational products, dose, and mode of administration: Test product: OLP-1002 Proposed dose levels for Part A: 30 ng, 120 ng, 400 ng, 1.2 µg, 3 µg, 6 µg, 12 µg, and 20 µg. Proposed dose levels for Part B: the doses for Part B will be decided in consultation with the Sponsor and on the basis of data from Part A of the study. The highest dose in Part B will be up to 50% of the highest dose in Part A. Administration route: subcutaneous
Reference product and mode of administration: Reference product: placebo Administration route: subcutaneous
Duration of subject participation in the study: Planned Screening duration: approximately 4 weeks. Planned study duration (Screening to Follow-up): approximately 8 weeks for Part A and approximately 12 weeks for Part B.

Endpoints:

Pharmacodynamics:

In Part A, the analgesic effect of OLP-1002 will be investigated in 3 groups consisting of 8 subjects (6 active: 2 placebo) using experimental capsaicin-evoked pain methods. Measurement of capsaicin-evoked pain will be performed at pre-screening, baseline and on Day 2, and secondary hyperalgesia at 5 and 30 minutes post-capsaicin injection. Continuous electrocardiogram (ECG) recording will be conducted to investigate the effect of OLP-1002 on cardiac function.

Safety:

Adverse events, clinical laboratory evaluations (clinical chemistry, hematology, urinalysis), 12-lead ECGs, vital signs measurements, injection site assessment, heat pain threshold and tolerance, and physical examinations.

Pharmacokinetics:

In Part A, the following PK parameters will be determined where possible: area under the plasma concentration-time curve (AUC) from time zero to infinity ($AUC_{0-\infty}$), AUC from time zero to the time of the last quantifiable concentration ($AUC_{0-t_{last}}$), maximum observed plasma concentration (C_{max}), time of the maximum observed plasma concentration (t_{max}), and apparent plasma terminal elimination half-life ($t_{1/2}$). PK analysis in Part A will initially only be conducted for groups receiving $\geq 12 \mu\text{g}$ OLP-1002, with retrospective analyses of samples from lower dose groups occurring in the event of PK data being quantifiable at doses $\geq 12 \mu\text{g}$ and if supported by bioanalytical stability data.

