3.1.2. Part B

Part B will comprise a multiple-dose, sequential-group study. Overall, 24 subjects will be studied in 3 groups (Groups B1 to B3), with each group consisting of 8 subjects. Up to 3 additional groups (24 subjects in total) may be included for further assessment of safety and tolerability ([Section 3.3](#)).

Potential subjects will be screened to assess their eligibility to enter the study within 28 days prior to the first dose administration. Each subject will participate in 1 treatment period only and reside at the CRU from Day -1 until Day 15.

All subjects will return for non-residential visits on Days 18 (± 2 days), 22 (± 2 days), 25 (± 2 days), and 29 (± 2 days), and for a poststudy visit on Day 57 (± 2 days).

[figure not shown]
In each of Groups B1 to B3, 6 subjects will receive OLP-1002 and 2 subjects will receive placebo. For all subjects, a single subcutaneous dose will be administered on Days 1, 4, 7, 10, and 13. Prior to each dosing occasion a physician will review the available safety and tolerability data from each subject to confirm it is acceptable to continue dosing. The dosing frequency in Part B may be changed following review of data from groups in Part A ([Section 3.4](#)).

Sentinel dosing will only occur in Part B at dose levels where exposure to OLP-1002 at steady state is predicted to exceed exposures that have been shown to be safe and well tolerated in earlier groups in Parts A or B. In the event of sentinel dosing, 2 subjects (1 active, 1 placebo) will be dosed at least 4 days prior to the remaining 6 subjects (5 active: 1 placebo). Safety data for the sentinel subjects from at least 2 additional doses will be reviewed prior to dosing the remaining subjects (i.e. sentinel subjects' safety data after doses 1 and 2 will be reviewed prior to the remaining subjects receiving dose 1). In addition, safety data from each subject will be reviewed by a physician prior to each dose to approve continued dosing.

Doses will be administered in an escalating manner following satisfactory review of safety, tolerability, and PK data up to Day 22 (216 hours post-final dose) from the lower dose levels. Part B may start after a review of the safety, tolerability, and available PK for Groups A1 to A6. The total daily dose administered will not exceed the highest single dose given in Part A.

An overview of the study design is shown in [Figure 2](#).

Figure 2: Study Schematic (Part B)

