Active = OLP-1002; SC = subcutaneous; TBC = to be confirmed.

All doses will be confirmed based on results of Part A; dose levels will not exceed the maximum proposed dose of 20 µg.

Groups B4 to B6 will be included if required.

The total duration of study participation for each subject (from Screening through Follow-up visit) is anticipated to be approximately 12 weeks.

A Schedule of Assessments is presented in [Appendix 6](#).

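### Part B dose ceilings: the 50% limit in Section 3.5.3 is followed by looser ceilings without saying which governs, and the stated bound of about 2-fold exposure holds only under the 50% limit

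*Protocol*

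**What the plan says.** Section 3.5.3 states that "the highest dose in the multiple-ascending-dose part will be up to 50% of the highest dose in the single-ascending-dose part", with the worked case of 20 µg in Part A giving 10 µg in Part B. It introduces this as a proposal. The reasons given are that concentrations may not be measurable and that the human prediction rests on one species. From the limit and a predicted accumulation of 3.7-fold it concludes that "the highest exposure in the multiple-ascending-dose part will not exceed ~2-fold the maximum exposure in the single-ascending-dose part". The version 2.1 synopsis repeats the limit without qualification: "The highest dose in Part B will be up to 50% of the highest dose in Part A".

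Other passages give other ceilings:

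- Section 3.5.3, next paragraph: "If additional groups (A9-11 or B3-6) are required, the maximum daily dose administered will not exceed 20" µg, subject also to the exposure limits of Section 3.7.
- Section 3.3: "The maximum dose for any additional group will not exceed 20 µg".
- Section 3.1.2 (version 2.1): "The total daily dose administered will not exceed the highest single dose given in Part A".
- Figure 2 footnote, about Part B only (version 2.1): "dose levels will not exceed the maximum proposed dose of 20" µg.

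Table 3 marks only B4 to B6 as optional, and Section 3.1.2 describes B1 to B3 as the planned groups. All Part B doses are still to be confirmed. Part B may open once Groups A1 to A6 have been reviewed; A6 is 6 µg.

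**The concern.** Every Part B dose will be fixed at meetings that work from this text. Section 3.7 lets no dose exceed 20 µg, so under the 50% limit no Part B dose can exceed 10 µg. The 20 µg figure and the Section 3.1.2 limit could then never bind on Part B. A reader who assumes that each stated limit does some work may take 20 µg as the operative limit for the groups it names. Because the list says B3-6, that reading reaches a planned group and not only the optional ones.

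The reference dose is also unclear. Section 3.5.3 speaks of the highest dose in the single-dose part without saying whether that is the dose planned or the dose already given and reviewed when a Part B decision is made. The two differ if Part B opens after A6.

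At stake is the one sentence in which the protocol says how far multiple dosing may go beyond the single-dose experience. It was written because pharmacokinetic data may not be able to show an excess.

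**Working it through.** **Inputs.** Human half-life 180 h, average interval 82 h and accumulation 3.7-fold (Section 3.5.2). Table 2 accumulation factors 2.28 for Cmax and 3.76 for AUC (Section 3.5.2). Default accumulation of 4-fold if exposure cannot be quantified (Section 3.4.1). Five doses on Days 1, 4, 7, 10 and 13, so 72 h apart (Section 3.1.2 in version 2.1, and Appendix 6). Exposure is taken as linear with dose, as Section 3.5.2 assumes.

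**Step 1: reproduce the protocol's accumulation.** Steady-state accumulation is R = 1/(1 − 2^(−τ/t½)). With τ = 82 h and t½ = 180 h, R = 3.69, which matches the stated 3.7.

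**Step 2: reproduce the bound.** Exposure multiple = R × (top Part B dose / top Part A dose). At 50%: 3.7 × 0.5 = 1.85. The figure of about 2-fold is reproduced.

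**Step 3: accumulation over the scheduled doses only.** After five doses, R = (1 − 2^(−5×72/180))/(1 − 2^(−72/180)) = (1 − 2^(−2))/(1 − 2^(−0.4)) = 3.10.

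**Step 4: apply each ceiling, with 20 µg as the top Part A dose.**

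| Accumulation factor | Source | Part B at 50% (10 µg) | Part B at 20 µg |
|---|---|---|---|
| 3.7 | Section 3.5.2 | 1.85 | 3.7 |
| 3.76 | Table 2, AUC | 1.88 | 3.76 |
| 4 | Section 3.4.1 default | 2.0 | 4.0 |
| 3.10 | five doses, step 3 | 1.55 | 3.10 |
| 2.28 | Table 2, Cmax | 1.14 | 2.28 |

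The protocol's own tables confirm the 20 µg column: AUC 3.15/0.837 = 3.76 and Cmax 0.294/0.129 = 2.28. The sentence in Section 3.5.3 uses 3.7, so the first row is the like-for-like comparison. On Cmax alone, 20 µg would lie close to 2-fold.

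**Step 5: compare with the Section 3.7 exposure limits.** At 20 µg multiple dosing, the Cmax margin is 24.9/0.294 = 85 and the AUC margin is 128/3.15 = 41, as Table 2 states.

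**Step 6: reference dose if Part B opens after A6.** Counting only doses already given, the 50% limit is 3 µg and the Section 3.1.2 limit is 6 µg. Counting planned doses, the 50% limit is 10 µg.

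**The case against.** The strongest reply is that these are nested upper bounds. Saying that a dose will not exceed 20 µg authorises no dose, and a team that always applies the strictest limit breaks no passage. A reader might infer that one passage permits a Part B dose which another forbids. The documents do not support that, because a cap is not a permission.

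There is also an innocent account of the 20 µg sentence. Amendment 1 added it as a restriction, and it covers A9-11 together with Part B groups, so its figure has to fit Part A. The 50% limit was already in version 1 and was kept. Section 3.1.2 speaks of total daily dose in a section that allows the dosing frequency to change, so it may be a backstop on a different quantity. This explains much of the text. It does not explain the Figure 2 footnote, which concerns Part B alone, or the listing of B3, and it still leaves unsaid which limit governs.

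A reader might also infer that 20 µg could be given in Part B when only 6 µg had been given in Part A. Section 3.1.2 rules that out, since its limit is tied to the highest single dose given. Nor should the multiple be pushed to 4.13, the steady-state value for indefinite dosing every 72 h, because the schedule stops at five doses.

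Finally, the 2-fold bound is not the only protection. The protocol also has sentinel dosing in Part B when predicted steady-state exposure exceeds what has been tolerated, physician review before each dose, a limit of 3-fold between dose levels above 120 ng, and the exposure stopping limits. All of that stands, and it lowers the urgency.

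**Conclusion.** This is an internal inconsistency that should be fixed. The statement of about 2-fold holds only under the 50% limit (1.85- to 2.0-fold on the protocol's 3.7, 3.76 and 4). At 20 µg it fails: 3.7- to 4.0-fold on the same factors, or about 3.1-fold for the five scheduled doses. These multiples assume linear exposure, a 180 h half-life and a top Part A dose of 20 µg.

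A reader might conclude that the looser ceilings breach the NOAEL-based limits. They do not: predicted margins at 20 µg remain 85-fold for Cmax and 41-fold for AUC. The conflict is with the protocol's own 2-fold bound.

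The 50% limit, the 20 µg figure for additional groups and the B3 listing are all in the current text of Sections 3.3 and 3.5.3 and Table 3. The Section 3.1.2 and Figure 2 ceilings are seen only in version 2.1. Amendment 3 lists no change to them, so they probably still apply, but this cannot be confirmed from what is shown.

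**What to change.** The sponsor and investigator must reconcile Sections 3.1.2, 3.3 and 3.5.3, the Figure 2 footnote and the synopsis, so that:

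1. one ceiling is stated to govern all Part B groups, core and additional;
2. the text says whether its reference is the Part A dose planned or the dose already given and reviewed;
3. the list B3-6 is brought into line with Table 3, which makes only B4 to B6 optional;
4. the exposure multiple that follows from the governing ceiling is restated, with the accumulation factor used.

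No ceiling is recommended here; that choice belongs to the sponsor and investigator. The cost is amendment wording only, with no change to sample size, assessments or analysis.
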